Head imaging will be obtained at baseline, at 4 ± 2 weeks after completion of radiation, and at subsequent follow-up visits every 2-4 months thereafter per usual clinical practice. Typically, this will consist with an MRI of the brain with contrast (although CT Head and non-contrast scans will be permitted if participants cannot receive standard MRIs). Head imaging will be used to define response as outline in section 12.7.

Follow-up data from these visits will continue to be collected after active participation in the study concludes. Therefore, participants will be followed per protocol for 6 months after completion of radiation treatment. Additional clinical follow up per standard of care will continue until death or loss to follow up, and relevant outcome data will be collected retrospectively during that time.

The length of follow up for the primary outcome measure (feasibility of receipt of fractions) will be 1 month after treatment completion. The length of follow up for all other endpoints will be until death or loss to follow up. This is because the usual clinical care for patients with brain metastases involves a radiation or neuro-oncology visit, history, and an MRI brain every 2-6 months until death or other loss to follow up.

Table 10. Study Calendar

	Visit 1	Visit 2	Visit 3	Visit 4	Visit 5	Visit 6	Every 2-4 months*
	Screening	Radiation Planning	Radiation Start	Week 1 Visit	Week 2 Visit	4-week follow up*	
Informed Consent	X						
Medical History (including assessment of development of seizures) & Physical Exam	X			X	X	X	X
Neurologic Exam	X			X	X	X	X
Karnofsky Performance Status (KPS)	X			X	X	X	X
CT or MRI	X	X				X	X
MDASI-BT	X					X	X
Toxicity Assessment	X			X	X	X	X
Radiation Planning		X					
Radiation Treatment			X	X	X		

*Patients who have significant transportation limitations may follow-up with their local oncologist and also forgo the MDASI-BT

Abbreviations: MDASI-BT: M. D. Anderson Symptom Inventory – Brain Tumor survey

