12. STATISTICAL CONSIDERATIONS

12.1 Study Design/Endpoints

Primary Endpoint

The primary outcome measure is the feasibility of delivering a model-adapted radiation fractionation schedule. Feasibility is defined as successful completion of radiation therapy for at least 13 of 14 patients. Successful completion of radiotherapy is defined as receipt of all scheduled fractions of daily radiotherapy within 24 hours of once daily fractions and within 1 hour of three-times daily fractions.

A sensitivity analysis has been performed on the mathematical model, which revealed no significant effect on tumor kill from the timing of once daily radiotherapy. This analysis did reveal the importance of the timing of three-times daily radiation therapy, for which feasibility was defined as treatment within 1 hour of the scheduled time.

Secondary Endpoints

Secondary outcomes and analytic techniques to assess these outcomes will include:

1. Quality of life, as determined by the MDASI-BT index (Appendix B), ascertained at the time of study enrollment, 4 weeks after completion of reirradiation, and every 2-4 months thereafter. We will conduct a longitudinal / repeated measures analysis to assess quality of life (mean MDASI-BT score for items 1-22 in APPENDIX B between 0-24 weeks)
2. Incidence (exact binomial distribution with 95% confidence intervals)

- and time to the development of Grade 3+ acute or delayed CNS toxicity
3. Incidence and time to development of radiation necrosis (Kaplan-Meier plot, Cox regression)
 4. Incidence and time to the development of seizures (Kaplan-Meier plot, Cox regression)
 5. Performance status (longitudinal regression)
 6. Overall survival, defined as the interval from registration to death from any cause (Kaplan-Meier plot, Cox regression)
 7. Progression-free survival, defined as the interval from registration to progression or death, whichever occurs first (Kaplan-Meier plot, Cox regression)
 8. Local recurrence, defined as the interval from registration to local recurrence (Kaplan-Meier plot)
 9. Incidence and time to salvage craniotomy (Kaplan-Meier plot, Cox regression)
 10. Incidence and time to additional systemic treatments after reirradiation (Kaplan-Meier plot)

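### Incidence of necrosis, seizures, salvage craniotomy and further systemic treatment is left to Kaplan-Meier with no rule for death; if deaths are censored, it is overstated

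*Combined protocol and SAP*

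**What the plan says.** Section 12.1 lists four secondary endpoints that ask for both an incidence and a time to an event other than death:

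- item 3: "Incidence and time to development of radiation necrosis (Kaplan-Meier plot, Cox regression"
- item 4: "Incidence and time to the development of seizures (Kaplan-Meier plot, Cox regression"
- item 9: "Incidence and time to salvage craniotomy (Kaplan-Meier plot, Cox regression"
- item 10: "Incidence and time to additional systemic treatments after reirradiation (Kaplan-Meier plot"

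None of them gives an estimator for the incidence, a time at which it is reported, or a rule for patients who die first. Section 12.7 adds response criteria and otherwise refers back to 12.1. Section 12.8 covers who is evaluable and how results are split by completion of radiotherapy. Competing risks are not mentioned anywhere.

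Other items in the same list are more specific. Item 2 (Grade 3+ CNS toxicity) names a method: "Incidence (exact binomial distribution with 95% confidence intervals". Item 6 gives an origin and an event: "Overall survival, defined as the interval from registration to death from any cause". Item 7 counts death as an event alongside progression.

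On follow-up, Section 10 states "The length of follow up for all other endpoints will be until death or loss to follow up", and also that "participants will be followed per protocol for 6 months after completion of radiation treatment".

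**The concern.** A patient who dies without necrosis can no longer develop it. Kaplan-Meier with that death censored treats the patient as still at risk, with the same future hazard as the survivors. One minus the Kaplan-Meier estimate (1-KM) then estimates the probability of the event in a setting where nobody dies. That exceeds the proportion of patients who actually have the event, and the gap grows with mortality.

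Mortality is high in this population, and the four endpoints describe the risks and the later treatment burden of a new re-irradiation schedule. Two analysts following Section 12.1 could report different rates from the same 14 patients, one from the curve and one as a crude proportion. A confidence interval around 1-KM would not reveal the difference, because the bias always runs upward.

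**Working it through.** **The plan's own figure.** The documents give no incidence, event rate or reporting time for these endpoints, so there is none to reproduce.

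**Inputs.**
- Sample size: 14 (Section 12.2).
- Median survival: 11 months in the re-irradiation series, and about 4 months from first progression (both Section 1.1).
- 1-KM at the reporting time: 20%. This is an assumption; a range is shown below.
- Constant, independent hazards: an assumption.

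**Formulas.** Death hazard m = ln 2 / median survival. Event hazard h = -ln(1 - 0.20)/t. Cumulative incidence CIF(t) = h/(h + m) × [1 - exp(-(h + m)t)]. Overstatement factor = (1-KM)/CIF.

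**Median 11 months**, m = 0.0630 per month (31.5% dead by 6 months, 53.1% by 12):
- t = 6: h = 0.0372; CIF = 0.3712 × 0.4519 = 16.8%; factor 20/16.77 = 1.19.
- t = 12: h = 0.0186; CIF = 0.2279 × 0.6244 = 14.2%; factor 20/14.23 = 1.41.

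**Median 4 months**, m = 0.1733 per month (64.6% dead by 6 months, 87.5% by 12):
- t = 6: CIF = 0.1767 × 0.7172 = 12.7%; factor 1.58.
- t = 12: CIF = 0.0969 × 0.9000 = 8.7%; factor 2.29.

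**Compared with sampling error.** SD = sqrt(p(1 - p)/14), with p the CIF.

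| Median survival | Time | Excess (points) | Excess × 14 (patients) | SD (points) |
|---|---|---|---|---|
| 11 months | 6 months | 3.2 | 0.45 | 10.0 |
| 11 months | 12 months | 5.8 | 0.81 | 9.3 |
| 4 months | 6 months | 7.3 | 1.0 | 8.9 |
| 4 months | 12 months | 11.3 | 1.6 | 7.5 |

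For scale, the exact 95% interval for 2/14 is 1.8% to 42.8%.

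**Sensitivity.**
- Event frequency matters little to the factor. For 1-KM of 10% to 50% it is 1.20 to 1.18 at 6 months and 1.42 to 1.37 at 12 months (median 11 months), or 1.59 to 1.52 and 2.34 to 2.13 (median 4 months).
- If the event raises the later death hazard 2 to 5 times, with overall median survival held at 11 months, the factor at 1-KM 20% falls to 1.17 to 1.13 at 6 months and 1.37 to 1.33 at 12 months.
- If no event can occur in the first 3 months (an assumption, for example for late necrosis), the factor at the 11-month median rises to about 1.32 at 6 months and 1.52 to 1.58 at 12 months.
- In simulated trials of 14 patients (1-KM 20%, median 11 months), the mean excess was 3.2 points at 6 months and 5.7 at 12 months. It reached 10 points in 4% and 18% of trials.

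**Time origin.** Items 6 to 8 count from registration. Section 12.8.1 makes patients evaluable for toxicity from first treatment, and its monitored list includes seizure and radiation necrosis. Item 10 counts treatments given after re-irradiation. No single origin is stated for the four items.

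**Item 8 (local recurrence).** It does not say whether death is an event. The progressive-disease criteria in Section 12.7 count failure to return because of death as progression. The two have to be reconciled.

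**The case against.** The strongest reply is that the bias is conditional. The plan lists a Kaplan-Meier plot, which may serve only the time-to-event half of each item, and an analyst could report x/14 beside it. With deaths known, x/14 has no such bias. This stands. A reader might infer from Section 12.1 that the plan commits to reading incidence from 1-KM; it does not say so. Equally, it names a crude proportion only for item 2, so for these four items the choice is open.

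A reader might also take 1.2 and 1.4 as the size of the error. They hold only for the 11-month median, which comes from a series of recurrent high-grade glioma rather than glioblastoma alone. Section 1.1's other median gives larger factors, so the result is a range.

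It would be tempting to say that items 3 and 4 have no time origin at all. Section 12.8.1 points to first treatment for both, without quite defining one. What is missing is a single stated origin.

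Two further points stand. Events graded 3 or higher as CNS toxicity are already covered by item 2's exact binomial, though item 2 gives no reporting time either. And with 14 patients the excess is usually small beside sampling error. It is not always so: at a 4-month median it exceeds the SD at 12 months (11.3 against 7.5 points). With 1-KM of 50% and an 11-month median it does so narrowly (50 - 36.6 = 13.4 against 12.9 points).

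**Conclusion.** The point holds in conditional form and is minor. Items 3, 4, 9 and 10 offer only Kaplan-Meier as a source of incidence for events that exclude death, in patients who are followed until death and often die early. If that curve is read with deaths censored, incidence is overstated. Under constant independent hazards and an assumed 1-KM of 20%, the factor is about 1.2 and 1.4 at 6 and 12 months with an 11-month median survival, and about 1.6 and 2.3 with a median of about 4 months.

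The consequence is confined to descriptive secondary reporting. A reader might infer that the feasibility result or the progression to a later trial is compromised. The documents do not support that: feasibility rests on completed fractions, and no decision rule uses these endpoints.

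**What to change.** In Sections 12.1 and 12.7:

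- For items 3, 4, 9 and 10, replace the Kaplan-Meier incidence curve with the Aalen-Johansen cumulative incidence, with death without the event as a competing event.
- Report it with a 95% CI at one stated time. Six months is an example that lies within per-protocol follow-up. Where every patient is followed to the event, death or that time, the estimate equals the crude proportion and item 2's exact binomial interval applies.
- State one time origin, reconciled with registration in items 6 to 8, first treatment in Section 12.8.1 and the after-re-irradiation wording of item 10.
- Interpret any Cox model for these items as cause-specific.
- For item 8, state whether death is an event and reconcile this with the failure-to-return criterion in Section 12.7. If death is not an event, use the same estimator.
- Leave the Kaplan-Meier analyses of overall and progression-free survival as they are.

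The cost is a few sentences and slightly more analysis work, with standard software and no new data.

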12.2 Sample Size and Power Justification

The final target accrual for this study will be 14 cases.

A recent trial attempted to deliver 90 fractions of radiation therapy to glioblastoma patients in 6 to 7 weeks, 5 days per week, 3 fractions per day (32). The schedule was successfully administered in 22/27 (81%) patients who started radiation therapy. The one-sided 95% upper limit (exact binomial distribution) for the population non-adherence was, therefore, 35%. Based on this adherence rate delivery of the schedule was deemed feasible.

The schedule proposed in this protocol is substantially simpler to deliver. If 13 out of 14 patients are able to complete the proposed schedule (86%), this study would demonstrate that the one-sided 95% upper limit (exact binomial distribution) for the population non-adherence is 30%. This non-adherence rate, or lower, would be deemed acceptable to progress to a subsequent efficacy trial. If all patients are able to complete the proposed schedule, this study would demonstrate that the one-sided 95% upper limit for the population non-adherence is no higher than 20%.

12.3 Sample Size, Accrual Rate and Study Duration

This study is expected to accrue 8-10 cases per year. Therefore, the target accrual should be completed within 22 months of study activation, allowing slow accrual in the first 6 months. If the average accrual over two months (6 months after trial activation) is less than 1 case, the study will be re-evaluated with respect to feasibility.

The study duration will be approximately 28 months; 22 months of accrual and 6 months of follow-up on the last participant enrolled.

Accrual should be well-balanced for males, females, and minorities.

Accrual Targets				
Ethnic Category	Sex/Gender			
	Females		Males	Total
Hispanic or Latino	1	+	1	= 2

Not Hispanic or Latino	6	+	6	=	12
Ethnic Category: Total of all subjects	7 (A1)	+	7 (B1)	=	14 (C1)
Racial Category					
American Indian or Alaskan Native	0	+	0	=	0
Asian	1	+	1	=	2
Black or African American	1	+	1	=	2
Native Hawaiian or other Pacific Islander	0	+	0	=	0
White	5	+	5	=	10
Racial Category: Total of all subjects	7 (A2)	+	7 (B2)	=	14 (C2)

(A1 = A2)

(B1 = B2)

(C1 = C2)

12.4 Stratification Factors

No stratification factors will be used in this non-randomized study. There will be no dose escalation in this cohort.

12.5 Interim Monitoring Plan

Futility: If two or more patients experience non-adherence events no further patients will be recruited.

12.6 Analysis of Primary Endpoints

Specified above

12.7 Analysis of Secondary Endpoints

Specified above

Local control will be defined as the interval from registration to local recurrence as determined by the Response Assessment in Neuro-Oncology (RANO) working group (33).

Response/Progression Categories

Complete response (CR). *All of the following criteria must be met:*

- Complete disappearance of all enhancing measurable and non-measurable disease sustained for at least 4 weeks. In the absence of a confirming scan 4 weeks later, this scan will be considered only stable disease.
- No new lesions.
- All measurable and non-measurable lesions must be assessed using the same techniques as baseline.
- Participants must be on no steroids or on physiologic replacement doses only.
- Stable or improved non-enhancing (T2/FLAIR) lesions.
- Stable or improved clinically, for clinical signs and symptoms present at baseline and recorded to be disease related.

Participants with non-measurable disease cannot have a complete response. The best response possible is stable disease.

Partial response (PR). *All of the following criteria must be met:*

- $\geq 50\%$ decrease compared to baseline in the sum of products of perpendicular diameters of all measurable enhancing lesions sustained for at least 4 weeks. In the absence of a confirming scan 4 weeks later, this scan will be considered only stable disease.
- No progression of non-measurable disease.
- No new lesions.
- All measurable and non-measurable lesions must be assessed using the same techniques as baseline.
- The steroid dose at the time of the scan evaluation should be no greater than the dose at time of baseline scan.
- Stable or improved non-enhancing (T2/FLAIR) lesions on same or lower dose of corticosteroids compared to baseline scan.
- Stable or improved, for clinical signs and symptoms present at baseline and recorded to be disease related clinically.

Participants with non-measurable disease cannot have a partial response. The best response possible is stable disease.

Progressive disease (PD). *The following criterion must be met:*

> 25% increase in sum of the products of perpendicular diameters of enhancing lesions (over best response or baseline if no decrease) on stable or increasing doses of corticosteroids and/or one or more of the of the following:

- Significant increase in T2/FLAIR non-enhancing lesion on stable or increasing doses of corticosteroids steroids compared to baseline scan or best response following initiation of therapy not due to co-morbid events (radiation therapy, demyelination, ischemic injury, infection, seizures, post-operative changes, or other treatment effects).
- Any new lesion

- Clear clinical deterioration not attributable to other causes apart from the tumor (e.g. seizures, medication side effects, complications of therapy, cerebrovascular events, infection, etc.). The definition of clinical deterioration is left to the discretion of the investigator but it is recommended that a decline in the Karnofsky Performance Score (KPS) from 100 or 90 to 70 or less, a decline in KPS of at least 20 from 80 or less, or a decline in KPS from any baseline to 50 or less, for at least 7 days, be considered neurologic deterioration, unless attributable to comorbid events or changes in corticosteroid dose.
- Failure to return for evaluation due to death or deteriorating condition
- *NOTE: If there is uncertainty whether the patient has progressed it is permissible to repeat the scan in 1 month. If that scan confirms progression, the date of progression will be the original date when progression was suspected to deal with ambiguities related to pseudoprogression.*

Stable disease (SD). *All of the following criteria must be met:*

- Does not qualify for CR, PR, or progression.
- All measurable and non-measurable sites must be assessed using the same techniques as baseline.
- Stable non-enhancing (T2/FLAIR) lesions on same or lower dose of corticosteroids compared to baseline scan. In the event that the corticosteroid dose has been increased, the last scan considered to show stable disease will be the scan obtained when the corticosteroid dose was equivalent to the baseline dose.
- Stable clinically.

Unknown response status.

- Progressive disease has not been documented and one or more measurable or non-measurable lesions have not been assessed.

These RANO Response Criteria are also summarized in the following table:

Table 11. Summary of RANO Response Criteria

	CR	PR	SD	PD
T1-Gad+	None	≥50% decrease	< 50% decrease – <25% increase	≥25% increase*
T2/FLAIR	Stable or decrease	Stable or decrease	Stable or decrease	Increase*
New Lesion	None	None	None	Present*
Corticosteroids	None	Stable or decrease	Stable or decrease	NA
Clinical Status	Stable or increase	Stable or increase	Stable or increase	Decrease*
Requirement for Response	All	All	All	Any

CR=complete response; PR=partial response; SD=stable disease; PD=progressive disease

#: Progression occurs when any of the criteria with * is present

NA: Increase in corticosteroids alone will not be taken into account in determining progression in the absence of persistent clinical deterioration.

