The predominant pattern of initial and subsequent failure in glioblastoma is local, with 75-93% of first recurrences occurring within the high-dose volume of radiotherapy (12–18). Accordingly, several prior studies have investigated intensification of local therapy. In the era before modern chemotherapy, such studies showed improved overall survival with conventionally fractionated radiation doses to 60 Gy over 45 Gy (19). However, efforts to dose-escalate further to 70 Gy (20) and 80 Gy (21) did not significantly improve survival or patterns of failure. Similarly, randomized studies investigating intensification of local therapy with stereotactic boosting (22) and brachytherapy (23) showed no improvement in outcomes.

Explanations for this paradoxical risk of local recurrence that is refractory to intensive local therapy have included intratumoral hypoxia, genomic and phenotypic heterogeneity, and limitations of current models of radioresistance. Conventionally “fractionated” radiation schedules are based largely on the linear-quadratic model which is commonly used to estimate the probability of tumor control and normal tissue complications (24). Despite good concordance with experimental results in other cancers (25,26), efforts to optimize radiation schedules based on the linear-quadratic model have not proven effective in the clinical setting for aggressive gliomas (27).

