2.3 Secondary Objectives

To evaluate patient-reported outcomes and patient satisfaction among participants receiving re-optimized radiation schedules.

To prospectively evaluate acute treatment-related toxicity from this re-optimized re-irradiation regimen.

To prospectively evaluate the following other endpoints among patients receiving this re-optimized re-irradiation regimen:

1. All-cause mortality

2. Incidence and time to local recurrence
3. Incidence and time to development of radiation necrosis
4. Incidence and time to salvage craniotomy
5. Incidence and time to systemic treatments after re-irradiation
6. Incidence and time to the development of seizures

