10. PARTICIPANT ASSESSMENTS

Table 10 presents the schedule of treatment and follow up visits. Visits should occur within 2 weeks of the scheduled day. If a participant fails to appear for a visit, the investigator will make every attempt to contact them and determine the reason for the missed visit. A participant will be deemed lost to follow-up only after at least 3 attempts to contact him/her have been made over a 4-week period. For participants who present with significant transportation or other barriers that would prevent them from being followed at the Dana-Farber/Brigham and Women's Cancer Center clinics, they may be followed closer to home at outside institutions by local oncologists, and clinical notes will be requested by the study team.

The primary endpoint (feasibility of receipt of fractions) will be assessed at the completion of all treatment fractions.

Medical history and physical exam, which includes general questions about health, medications being taken, current allergies, and assessment of the development of seizures will be taken at

screening, at each weekly visit during radiation therapy, at 4 ± 2 weeks after completion of radiation, and at subsequent follow-up visits every 1-3 months thereafter per usual clinical practice.

Karnofsky Performance Status (KPS) will be assessed at screening, at each weekly visit during radiation, at 4 ± 2 weeks after completion of radiation, and at subsequent follow-up visits every 2-4 months thereafter per usual clinical practice.

Toxicity review will consist of a history at each visit to monitor for relevant toxicity as described in section 9. Toxicity will be assessed at each weekly visit during radiation therapy, at 4 ± 2 weeks after completion of radiation, and at subsequent follow-up visits every 2-4 months thereafter per usual clinical practice.

Quality of life, as per the MDASI-BT: M. D. Anderson Symptom Inventory – Brain Tumor survey) will be assessed at baseline, at 4 ± 2 weeks after completion of radiation, and at subsequent follow-up visits every 2-4 months thereafter per usual clinical practice. The MDASI-BT is performed as part of an institution-wide effort to collect patient-reported outcomes. This is the usual care pattern for such patients. Patients who have significant transportation limitations may follow-up with their local oncologist and forgo the questionnaire.

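### Local recurrence is not tied to the re-irradiated volume, and the plan does not say how deaths or lesions judged necrotic enter its incidence

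*Combined protocol and SAP*

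**What the plan says.** Section 2.3 lists "Incidence and time to local recurrence" and "Incidence and time to development of radiation necrosis" as separate secondary objectives. Section 12.1, item 8, gives the endpoint as "Local recurrence, defined as the interval from registration to local recurrence (Kaplan-Meier plot"; no other method is named for it. Section 12.7 calls the same interval local control: "Local control will be defined as the interval from registration to local recurrence as determined by the Response Assessment in Neuro-Oncology (RANO) working group".

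Section 12.7 then reproduces RANO response categories. Progressive disease is met by "> 25% increase in sum of the products of perpendicular diameters of enhancing lesions" or by any of four other triggers: T2/FLAIR increase, a new lesion, clinical deterioration, or failure to return because of death or worsening condition. The T2/FLAIR trigger excludes treatment effects, and the clinical trigger excludes complications of therapy. A note after the list permits a repeat scan at one month when progression is uncertain, with the date set back to the first suspicion if confirmed.

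Section 12.8.1 provides for enhancing lesions that grow after radiation to be assessed for necrosis by PET, at the clinicians' discretion. On follow-up, section 10 says: "The length of follow up for all other endpoints will be until death or loss to follow up".

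**The concern.** The word local shows that a site restriction is intended, but the plan never says local to what. Section 6.4.1.3 defines a PTV, and no passage refers a recurrence back to it. The reproduced criteria sum lesions over the brain or have no site at all. An assessor who follows them literally would record a distant-only lesion, or a purely clinical decline, as a local recurrence. A second assessor who restricts by site would not, and the two could report different rates from the same records.

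Two further gaps affect the same endpoint. Incidence is an objective, yet the only named analysis is a Kaplan-Meier plot, in a population followed to death. Also, growth of an enhancing lesion is both a progression trigger and the prompt for the necrosis work-up, with no rule on how a necrosis finding changes the recurrence record. At stake are two named secondary objectives. The primary feasibility endpoint and the futility rule are untouched.

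**Working it through.** The plan gives no local recurrence figure to reproduce, so the check compares the text and then bounds the size.

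**1. Location.** The site content of each reproduced trigger in section 12.7:

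| Trigger | Tied to the PTV? | Treatment effect excluded? |
|---|---|---|
| Enhancing-lesion sum | No | No |
| T2/FLAIR increase | No | Yes |
| New lesion | No | No |
| Clinical deterioration | No site | Yes (complications of therapy) |
| Failure to return | No site | Not stated |

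Table 11 requires any one starred criterion for progression, so a single trigger without a site is enough.

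**2. Size of the location gap.** Inputs: N = 14 (section 12.2) and "75-93% of first recurrences occurring within the high-dose volume of radiotherapy" (section 1.1), which leaves 1 − 0.93 = 7% to 1 − 0.75 = 25% outside. Assumption: this pattern, described for glioblastoma in general, carries over to re-irradiation.

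- One patient: 1/14 = 7.1 percentage points.
- All 14 recur: 14 × 0.07 = 0.98 and 14 × 0.25 = 3.50 patients, or 7.0 and 25.0 points.
- 7 of 14 recur: 7 × 0.07 = 0.49 and 7 × 0.25 = 1.75 patients, or 3.5 and 12.5 points.

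The all-recur case is a ceiling. It requires every out-of-field failure to be called local and none of those patients to fail locally later. It covers location only; the documents give no rate for clinical-only progression.

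**3. Death.** Item 7 of section 12.1 defines progression-free survival with death as an event. Item 8, the next line, does not mention death. The intended reading is that death is not a local recurrence. Whether it is censored or competing is not stated.

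**4. Estimator.** Let a be the hazard of local recurrence and b the hazard of death without it, both constant. With deaths censored, 1 − KM at time t is 1 − exp(−a·t). The cumulative incidence is a/(a+b) × [1 − exp(−(a+b)·t)]. The first is larger whenever b > 0.

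An invented sequence of 14 patients, with 6 recurrences (R), 3 deaths without recurrence (D) and no other censoring, shows the mechanism. In the order R, D, R, R, D, R, R, D, R, with five event-free:

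- KM = 13/14 × 11/12 × 10/11 × 8/9 × 7/8 × 5/6 = 0.502, so 1 − KM = 49.8%.
- Cumulative incidence = 6/14 = 42.9%.

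The gap here is 7.0 points. With the two median survivals cited in section 1.1 (about 4 and 11 months), assumed median times to local recurrence of 4, 6 or 9 months, and an assumed 25% to 100% of the death hazard acting before recurrence, the gap runs from 2 to 21 points at 6 months and from 5 to 38 at 12 months. The assumed inputs are not in the documents, so these ranges illustrate direction and sensitivity only.

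**5. Necrosis.** An enhancing lesion that grows by more than 25% meets the progression trigger and also enters the section 12.8.1 work-up. The repeat-scan note addresses uncertainty about progression, but it is optional and does not say that a lesion judged necrotic is not a recurrence. The same lesion can therefore be counted under both objectives.

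**The case against.** The strongest reply is that the intent is clear enough. Local implies a site, items 7 and 8 differ on death, the note deals with pseudoprogression, and RANO is incorporated by a citation that may contain more than the text reproduces. Item 8 also does not say that incidence will be read from one minus Kaplan-Meier. It could be a simple proportion, as item 2 uses an exact binomial method for toxicity incidence. This is one of ten secondary endpoints in a 14-patient single-arm study, with no test or decision attached.

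Much of this stands, and it rules out several stronger readings:

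- A reader might infer that deaths will be scored as local recurrences because failure to return through death is on the progression list. The contrast between items 7 and 8 points the other way.
- A reader might infer that section 12.7 contradicts itself because Table 11 omits failure to return. The table is presented as a summary, so the omission is not a rival rule.
- A reader might infer that treatment effect is ignored. Two triggers exclude it, and the note allows a repeat scan.
- A reader might infer that follow-up for local recurrence could stop at distant progression. Section 10 carries it to death or loss.

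What the reply does not supply is a site definition, a stated role for death, a method for incidence, or a rule for lesions judged necrotic. Intent alone does not tell an assessor whether a marginal lesion is local.

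**Conclusion.** The point holds as a gap in endpoint definition and estimation. The reproduced criteria apply to the whole patient, no passage ties an event to the re-irradiated PTV, and incidence is requested without a stated method that handles death.

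On location, 1.0 to 3.5 of 14 patients (7.0 to 25.0 percentage points) is an upper bound that assumes the section 1.1 pattern carries over and all patients recur. It should not be read as an expected error. The estimator bias is conditional: it arises if deaths are censored and one minus Kaplan-Meier is reported as incidence, and its size cannot be derived from the documents. The finding concerns the text as reproduced; the cited RANO source was not available. Only secondary descriptive endpoints are affected. Severity is minor to moderate.

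**What to change.** - **Section 12.7:** define local recurrence as RANO imaging progression inside or contiguous with the re-irradiated PTV. Keep the full progression list for progression-free survival. State that death and distant-only or clinical-only progression are not local recurrence events.
- **Section 12.1, item 8:** report cumulative incidence with death as a competing event. Use the same estimator for the other non-fatal time-to-event incidences (items 3, 4, 9, 10 and the time-to-event part of item 2), so that the list stays consistent.
- **Necrosis:** for analysis, count a lesion judged necrotic on PET or pathology already obtained for care as necrosis and not as recurrence. Report undetermined lesions separately.

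The cost is SAP wording and one location check per progression event, for at most 14 patients, with no added visits or scans. Final dosimetry information is already submitted (section 11.2); that the PTV can be retrieved from it is an assumption. For patients with barriers to attending, section 10 says "they may be followed closer to home at outside institutions by local oncologists, and clinical notes will be requested by the study team", so for some of them the site may have to be classed as undetermined.
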